**The Effect of Virtual Reality on Pain,
Physical Function, and Health-Related
Quality of Life in Children with
Sickle Cell Disease: A Randomized
Controlled Trial**

NCT05952817

STUDY PROTOCOL

May 2025

Title: The effect of virtual reality on pain, physical function, and health-related quality of life in children with sickle cell disease: A randomized controlled trial

Significance or rationale of the study:

Virtual reality (VR) is a promising non-pharmacological pain management tool. It enhances motor function by promoting cortical reorganization and neuroplasticity. Its multimodal biofeedback engages sensory and cognitive functions, making therapy interactive, motivating, and easy to understand. With strong rehabilitation potential, VR helps patients adapt to real-world movements (Laver, 2020). Initially used for procedural pain management, VR is now expanding into chronic pain rehabilitation by encouraging engagement with difficult or avoided movements (Griffin et al., 2020). Additionally, VR offers a dynamic alternative to traditional exercises, improving adherence and outcomes. Integrating entertainment into therapy can motivate children, enhancing their physical and psychological well-being. Recently, a few studies revealed an improvement in vaso-occlusive episodes (VOE) after VR treatment (Agrawal et al., 2019). However, efficacy studies are needed to assess VR's potential benefits. Additionally, data regarding VR's efficacy on daily pain, functional mobility, and HRQOL as complementary therapy are limited

The objectives: This study aimed to assess the impact of VR on daily pain, functional mobility, and HQOL

Methods: In this single-blind Randomized Controlled Trial (RCT), 42 children aged 8 to 13 with SCD were included. They were divided into an intervention group (group I, n=21) and a control group (group II, n=21). Group I received one session of fully immersive VR for 15 minutes during hospitalization (Phase One). After discharge (Phase Two), Group I participants received fully immersive VR for 40 minutes twice /week over three weeks (six sessions) besides

medications. Yet, Group II received the prescribed drugs. Pain intensity was measured using the Numeric Rating Scale (NRS), and functional mobility was assessed with the Time UP and GO TUG test. The PedsQLTM 3.0 SCD module was used to measure the PedsQL.

Outcomes: Investigate VR's effect on reducing daily pain in children with SCD and evaluate its impact on improving functional mobility in these children.

Examine the changes in PedsQL in children with SCD after engaging in VR experiences. 5- To evaluate the safety and satisfaction of fully immersive VR therapy in children with SCD.

Statistics: Data were analyzed using IBM SPSS Statistics Version 29.0. Descriptive statistics (means, standard deviations, frequencies, and percentages) were calculated to summarize demographic and baseline characteristics. The normality of continuous variables was assessed using the Kolmogorov-Smirnov test.

Due to the non-normal data distribution, the Mann-WhitneyU test was used to compare pain intensity scores measured by the Numeric Rating Scale (NRS) between intervention and control groups. Within-group comparisons of pre- and post-intervention scores were also conducted.

Safety outcomes from the Simulator Sickness Questionnaire were analyzed using the Chi-square test to detect any significant changes in symptoms pre- and post-intervention.

Satisfaction scores from the VR Satisfaction Likert survey were analyzed descriptively, and the Mann-Whitney U test was applied to compare satisfaction across age groups.

A significance level of $p < 0.05$ was used for all inferential statistical tests.

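### The only between-group pain test described makes no use of baseline; if NRS was recorded in both groups before Phase One, add one supportive baseline-adjusted comparison per phase

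*Combined protocol and SAP*

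**What the plan says.** All of the following is in the combined protocol and SAP.

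- The objectives paragraph puts daily pain first: "This study aimed to assess the impact of VR on daily pain, functional mobility, and HQOL".
- Methods gives the arm sizes: "They were divided into an intervention group (group I, n=21) and a control group (group II, n=21"). It describes two phases. The first is in hospital: "Group I received one session of fully immersive VR for 15 minutes during hospitalization (Phase One"). The second is six sessions over three weeks after discharge. No NRS measurement times are given for either phase.
- Statistics gives the between-group pain analysis: "the Mann-WhitneyU test was used to compare pain intensity scores measured by the Numeric Rating Scale (NRS) between intervention and control groups". The reason offered for a rank test is "Due to the non-normal data distribution".
- The next sentence reads "Within-group comparisons of pre- and post-intervention scores were also conducted". It names neither the instrument nor the phase.
- Descriptive statistics "were calculated to summarize demographic and baseline characteristics". Whether NRS was among these characteristics is not said.
- The paragraph is in the past tense: "Data were analyzed using IBM SPSS Statistics Version 29.0".

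**The concern.** The effect of VR on pain rests on the contrast between randomised groups. As described, that contrast uses no baseline information, although a score from before the intervention was apparently available. Within-group comparisons do not fill the gap, because they do not use the randomised contrast.

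Two things follow with 21 per arm. First, if baseline pain predicts later pain, the interval for the treatment difference is wider than it need be. Second, one arm may start with more pain by chance. A test on post values and a test on changes then respond differently, and the text does not say which was run. For the first-listed objective, a reader cannot judge how far an observed difference reflects the starting point.

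**Working it through.** **Inputs from the documents.** 21 per arm (Methods) and a 0.05 significance level (Statistics; two-sided is assumed). There is no power, SD, effect size or correlation, so the plan has no figure of its own to reproduce.

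**Assumed inputs.** Integer NRS from 0 to 10, SD 2 before and after, baseline mean 6, control post mean 5, pre/post correlation ρ of 0, 0.3, 0.5 or 0.7.

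**Step 1: CI width by formula.** The standard error factor is √(2/21) = 0.3086.

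- Unadjusted half-width = t(40 df) × 2 × 0.3086 = 2.021 × 2 × 0.3086 = 1.25 points.
- Adjusted half-width = t(39 df) × 2 × 0.3086 × √[(1 − ρ²)(1 + 1/38)], with t = 2.023. The factor 1 + 1/38 is the cost of estimating the covariate slope.

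| ρ | Adjusted, formula | Change | Adjusted, simulated (unadjusted 1.24) | Change | Equivalent n per arm |
|---|---|---|---|---|---|
| 0 | 1.26 | +1% | 1.26 | +1% | 20.5 |
| 0.3 | 1.21 | −3% | 1.20 | −3% | 22.5 |
| 0.5 | 1.10 | −12% | 1.10 | −12% | 27.3 |
| 0.7 | 0.90 | −28% | 0.92 | −26% | 40.1 |

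The simulation used 20,000 trials per cell with scores rounded and clipped to 0–10. It shows slightly less gain at 0.7 because rounding lowers the observed correlation to about 0.68. Equivalent n is 21/[(1 − ρ²)(1 + 1/38)]. In variance terms the break-even is ρ = √(1/39) = 0.16. If 42% of controls score zero, the changes in width shrink to +1, −2, −8 and −19%.

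**Step 2: validity.** Over all simulated null settings, type I error was 4.5–5.3% for Mann-Whitney (on post values or changes) and 4.8–5.4% for linear ANCOVA. Coverage of the linear ANCOVA 95% CI was 94.6–95.2% over 36 settings, including those with many scores at the scale floor.

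**Step 3: chance imbalance.** The difference in baseline means has SE 0.3086 SD. Given a gap of g, the expected null difference is ρg in post values and −(1 − ρ)g in changes. For g = 0.5 SD = 1 point:

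| ρ | Post values | Changes |
|---|---|---|
| 0 | 0 | −1.0 |
| 0.3 | +0.3 | −0.7 |
| 0.5 | +0.5 | −0.5 |
| 0.7 | +0.7 | −0.3 |

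The two err in opposite directions only when ρ lies strictly between 0 and 1. A gap between 0.4 and 0.6 SD has probability 2[Φ(0.6/0.3086) − Φ(0.4/0.3086)] = 0.14. Within that band, at ρ = 0, 0.3, 0.5 and 0.7, simulated type I error was:

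- Mann-Whitney on post values: 4.9, 6.1, 8.4 and 11.0%
- Mann-Whitney on changes: 11.3, 9.8, 8.6 and 7.1%
- ANCOVA on ranks: 5.0–5.3%

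These conditional figures were obtained for the rank version of ANCOVA, not the linear one.

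**The case against.** The strongest reply is that an unadjusted rank test is a legitimate analysis of a randomised trial, so an extra analysis that cannot replace it is partly a matter of preference. The first half stands: validity is not in question. The second half is weaker, because the adjusted estimate gives an interval in NRS points and a check on imbalance at very small cost.

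It is also fair that the benefit rests on two unknowns: whether a pre-Phase-One NRS exists in both groups, and the correlation. For daily pain, the baseline would be an in-hospital score and the outcome a score three weeks into the post-discharge phase. The correlation may be low, and from 0 to 0.3 the width changes only by +1% to −3%. This stands and is why the request is conditional and supportive.

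Three stronger readings are tempting, and the documents support none of them:

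- *That pre-intervention NRS was used only within groups.* The within-group sentence does not name NRS, and the between-group sentence gives no time point, so a between-group comparison of starting scores is not excluded.
- *That the Mann-Whitney result is biased or invalid.* Over all randomisations its error rate is about 5%; the inflation in step 3 is conditional on an observed gap.
- *That the trial gave up a stated amount of power.* The analysis is reported as done, so planned power cannot now be recovered. What remains available is a narrower interval and a check on imbalance.

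Finally, the document is very short. The most that can be said is that adjustment is not described here.

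**Conclusion.** The point holds as one of precision and robustness. The described between-group pain test is valid, but it has no baseline term and its score type and time point are unstated. The size ranges from a CI about 1% wider at zero correlation to about 26% narrower at 0.7, with little change below about 0.3. This rests on an assumed SD of 2, equal variances and 21 children analysed per arm; the documents supply only the arm size. Confidence is medium, because neither the correlation nor the existence of a pre-Phase-One NRS in both groups can be established from the text. The point is worth acting on because the possible gain is material and the worst-case loss is small.

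**What to change.** 1. In the sentence that reports the Mann-Whitney test, state whether it used post values or changes, and at which time point in which phase.
2. If NRS was recorded in both groups before Phase One, report beside it one supportive comparison per phase. Possible wording: *Supportive post hoc analysis: NRS at the end of each phase was compared by linear ANCOVA with group and pre-Phase-One NRS as terms; the adjusted mean difference and its 95% CI are given.* Drop the post hoc label only if outcome data are in fact unseen.
3. Let the linear ANCOVA estimate be the adjusted result that governs. ANCOVA on ranks may be added only as a sensitivity check on its p-value.
4. Keep Mann-Whitney as the stated analysis. If the results differ, report both and do not switch.
5. Do not use a score from the start of Phase Two as baseline. It follows the first VR session in Group I and may already reflect treatment.
6. If no pre-Phase-One NRS exists in both groups, say so as a limitation.

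**Cost.** One sentence of wording and one short SPSS linear model per phase (two if the rank check is added), with no new data. The downsides are the post hoc label and a CI about 1% wider if the correlation is zero. Without the baseline score, the cost is one limitation sentence.

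### The only between-group efficacy analysis the plan names is a Mann-Whitney test on NRS pain, with no effect estimate or confidence interval

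*Combined protocol and SAP*

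**What the plan says.** The objectives paragraph sets the aim: "This study aimed to assess the impact of VR on daily pain, functional mobility, and HQOL". For pain, the Statistics paragraph states that "the Mann-WhitneyU test was used to compare pain intensity scores measured by the Numeric Rating Scale (NRS) between intervention and control groups", because the data were not normally distributed. The 0.05 level "was used for all inferential statistical tests".

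The other analyses named are:

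- **Descriptive statistics:** these "were calculated to summarize demographic and baseline characteristics".
- **Within-group change:** "Within-group comparisons of pre- and post-intervention scores were also conducted". The test is not named.
- **Simulator sickness:** "analyzed using the Chi-square test to detect any significant changes in symptoms pre- and post-intervention".
- **Satisfaction:** summarised descriptively, and "the Mann-Whitney U test was applied to compare satisfaction across age groups".

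None of these four estimates a difference between the VR and control arms. The Methods paragraph gives 42 children, 21 per arm, and two phases: a single in-hospital session, then six sessions after discharge. The Statistics paragraph does not say at which phase or time point NRS is compared, or whether post-treatment scores or changes are compared.

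**The concern.** An aim of assessing impact calls for a magnitude. The Mann-Whitney statistic and its p-value are not in NRS points. Carried out exactly as described, the plan shows whether the arms differ at the 5% level, but not by how much or how precisely that is known. The within-group comparisons cannot fill the gap, because pain may change over time in both arms and a change within one arm does not isolate the effect of VR.

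Two things are at stake. A significant result without a size cannot show whether the reduction is worth having. A non-significant result without an interval cannot separate no effect from a useful effect measured imprecisely, and with 21 per arm the second is quite possible.

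**Working it through.** The plan has no power statement, target difference or standard deviation, so there is no figure of its own to reproduce. The check asks how much a bare p-value leaves unsaid at this sample size.

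**Inputs from the documents.** n = 21 per arm (Methods); alpha = 0.05 (Statistics).

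**Assumptions.** Two-sided testing (sidedness is not stated); NRS standard deviation (SD) 1.5 to 3 points; a true benefit of 1 point; 2 points as an illustrative threshold for a benefit of interest.

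**Step 1: precision of a mean difference, in SD units.** The 95% half-width is t(0.975, 40) × √(2/21) = 2.021 × 0.3086 = 0.62 SD. For SDs of 1.5, 2, 2.5 and 3 this is 0.94, 1.25, 1.56 and 1.87 points.

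**Step 2: detectable difference.** At 80% power, (1.960 + 0.842) × √(2/21) = 0.86 SD. Dividing by √(3/π) for the Mann-Whitney test gives 0.88 SD.

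**Step 3: Hodges-Lehmann interval.** There are 21 × 21 = 441 pairwise differences. The standard error of U is √(21 × 21 × 43 / 12) = 39.75. The lower limit is the K-th smallest difference, with K = 220.5 − 1.96 × 39.75 = 142.6, rounded down to 142. The upper limit is the 142nd largest.

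**Step 4: simulation.** Scores were drawn from normal distributions with means 5 (control) and 4 (VR), rounded to whole numbers and truncated to 0–10. There were 4,000 trials per setting. An interval counts as reaching 2 points if its upper limit is 2 or more.

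| Assumed SD | Mean half-width of 95% interval (points) | Non-significant | Of those, interval reaches 2 points |
|---|---|---|---|
| 1.5 | 0.98 | 47% | 68% |
| 2 | 1.29 | 68% | 82% |
| 2.5 | 1.59 | 77% | 89% |
| 3 | 1.84 | 83% | 90% |

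A separate run of 3,000 trials per setting gave 48%, 68%, 77% and 83% non-significant, with 66%, 81%, 88% and 90% of those reaching 2 points. The two runs agree within about 2 percentage points.

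**Step 5: what the interval adds.** With no true difference, the share of non-significant trials whose interval reaches 2 points is 13%, 37%, 55% and 65% for the same four SDs. At SD 1.5, then, the interval reaches 2 points in 13% of non-significant trials when VR does nothing, against 68% when it lowers pain by 1 point. The bare verdict p ≥ 0.05 is the same in both cases. At SD 3 the contrast narrows to 65% against 90%, and the interval then mainly shows how little the trial can rule out.

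**The case against.** The strongest reply is that this is brevity. The section names a test, not the tables to be reported. It does not say that descriptive statistics were confined to baseline, or that a p-value is the only output. The authors may well report medians by arm. This stands in part: a reader might infer that the plan forbids outcome summaries, and it does not. But the section presents a test as the analysis carried out, and nothing in it commits anyone to an estimate.

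Second, the non-significance rates reflect sample size, and adding an interval does not change them. That is correct. They also depend on an assumed SD. At SD 1.5 about half of trials are non-significant, so the tempting statement that a null result would be the usual outcome of a modest benefit does not hold across the range. The rates show why an interval is needed; they do not measure what it would cure.

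Third, on a bounded whole-number scale the Hodges-Lehmann estimate assumes a common shift that can hold only approximately. Pairwise differences of whole numbers are themselves whole numbers, so the interval in any one trial is coarse. This stands, and should be acknowledged when the result is reported.

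Finally, the plan names no between-group analysis at all for the TUG test or PedsQL, which is arguably a larger gap. It is a separate matter and does not lessen this one.

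**Conclusion.** The point holds as a cheap improvement. The named between-group analysis is a test without an estimate or interval, so the output as written does not give the size of VR's impact on pain. At 21 per arm, a non-significant result could be misread as no effect. Across assumed SDs of 1.5 to 3, the interval is about ±1.0 to ±1.8 points. With a true 1-point benefit, about 48% to 83% of trials are non-significant, and about 66% to 90% of those have an interval still reaching 2 points. The SD, the 1-point benefit, the 2-point threshold and two-sided testing are all assumptions.

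Two stronger readings are not supported. A reader might infer that the trial cannot state the impact of VR on pain, but the same 42 children can supply the estimate. A reader might also infer that a null result will be misreported, but nothing in the documents says how p ≥ 0.05 will be interpreted. Nor does this show that the Mann-Whitney test is the wrong test.

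**What to change.** Keep the Mann-Whitney test and add to the Statistics section:

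> For each phase, the between-group difference in NRS is reported at one named time point (after the in-hospital session, and after the six post-discharge sessions) as the Hodges-Lehmann difference in points with its 95% confidence interval, alongside the Mann-Whitney p-value. Medians and quartiles are given by arm. Conclusions are drawn from the interval, and p ≥ 0.05 is not reported as absence of effect.

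The exact time point within each phase has to be filled in. If a baseline-adjusted model is adopted, state in advance which estimate is primary, so that two estimates do not compete.

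The cost is a few lines of wording and output, with no new children, visits or data. The downsides are that the interval will show openly how imprecise 42 children are, and that ties on a bounded 0–10 scale make the shift approximate.

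### Change in simulator-sickness symptoms is tested with a chi-square test; unless this loosely means McNemar's test, an independence test is applied to what appear to be paired answers

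*Combined protocol and SAP*

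**What the plan says.** Safety is a listed aim under Outcomes: "To evaluate the safety and satisfaction of fully immersive VR therapy in children with SCD". The Statistics section gives it one inferential analysis: "Safety outcomes from the Simulator Sickness Questionnaire were analyzed using the Chi-square test to detect any significant changes in symptoms pre- and post-intervention".

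The Methods section sets out who was exposed. On allocation: "They were divided into an intervention group (group I, n=21) and a control group (group II, n=21". In hospital, "Group I received one session of fully immersive VR for 15 minutes during hospitalization (Phase One"; after discharge, "Group I participants received fully immersive VR for 40 minutes twice /week over three weeks (six sessions". For the controls: "Yet, Group II received the prescribed drugs". So VR was given to 21 children, in 1 + 6 = 7 sessions each.

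The only other mention of a before/after analysis follows the pain-score sentence: "Within-group comparisons of pre- and post-intervention scores were also conducted". It names no test. The document does not say who completed the sickness questionnaire, whether its items were reduced to present/absent, or which of the seven sessions define before and after.

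**The concern.** The stated purpose is "to detect any significant changes in symptoms pre- and post-intervention". That is a question about change within a child, and only one arm was exposed to VR, so the two sets of answers are most naturally paired. Pairing is an inference here; the document does not state it.

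An ordinary chi-square test could have been applied to such data in two ways.

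- **Stacked.** The 21 answers before and the 21 after are treated as two independent samples. The test ignores the covariance between a child's two answers. With positive correlation its variance is too large and the test is mainly conservative.
- **Cross-tabulated, before by after.** The test then asks whether the two answers are associated, not whether symptoms changed. Nothing in the text shows that this layout was used, so it is a secondary risk.

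For a harm outcome, lost sensitivity is the unfavourable direction: a non-significant result would be read as evidence that VR is well tolerated.

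**Working it through.** The plan gives no figure to reproduce: no symptom rates, no power statement and no sample-size calculation.

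**Inputs from the document.** 21 VR children; significance level 0.05.

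**Assumptions.** All 21 answered twice; symptom present or absent; two-sided testing; prevalence and within-child (phi) correlation ρ as shown.

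**Why stacking is conservative.** For rates p₁ before and p₂ after, the variance of the difference in proportions is

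[p₁(1−p₁) + p₂(1−p₂) − 2ρ√(p₁(1−p₁)p₂(1−p₂))] / n.

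The stacked test drops the last term. With no change this reduces to 2p(1−p)(1−ρ)/n, against 2p(1−p)/n assumed by the stacked test. At ρ = 0.5 the assumed variance is therefore twice the true one.

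**Exact rejection rates.** All paired 2×2 tables with n = 21 were enumerated. Cell probabilities were p₁₁ = p₁p₂ + ρ√(p₁(1−p₁)p₂(1−p₂)), p₁₀ = p₁ − p₁₁, p₀₁ = p₂ − p₁₁, and the remainder for neither.

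False positives with no true change, at ρ = 0 / 0.2 / 0.5:

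| Test | 30% prevalence | 10% prevalence |
|---|---|---|
| Stacked Pearson | 5.6 / 3.3 / 0.8% | 4.1 / 2.2 / 0.5% |
| McNemar, asymptotic | 4.3 / 4.6 / 4.7% | 4.2 / 3.2 / 1.2% |
| McNemar, mid-p | 4.1 / 3.7 / 2.1% | 1.5 / 0.9 / 0.2% |
| McNemar, exact | 2.1 / 1.7 / 0.6% | 0.4 / 0.2 / 0.02% |

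Power, at ρ = 0 / 0.1 / 0.2 / 0.3:

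| Test | 25% to 60% | 5% to 30% |
|---|---|---|
| Stacked Pearson | 64.1 / 64.9 / 65.7 / 66.6% | 61.7 / 62.1 / 62.5 / 62.8% |
| McNemar, asymptotic | 59.7 / 64.5 / 70.4 / 77.7% | 57.4 / 62.7 / 69.0 / 76.5% |
| McNemar, mid-p | 59.7 / 64.4 / 70.0 / 76.5% | 51.8 / 54.7 / 57.9 / 61.4% |
| McNemar, exact | 49.8 / 54.2 / 59.4 / 65.7% | 37.4 / 39.1 / 40.8 / 42.5% |

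Stacked Pearson and asymptotic McNemar break even near ρ = 0.1.

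**Example 1: six new symptoms, none resolved, 5 children symptomatic before and 11 after.**

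- Stacked Pearson: pooled rate 16/42 = 0.381; χ² = (6/21)² / (0.381 × 0.619 × 2/21) = 3.63, p = 0.057.
- Asymptotic McNemar: (6 − 0)²/(6 + 0) = 6.0, p = 0.014.
- Exact McNemar: 2 × 0.5⁶ = 0.031, against Fisher 0.11.

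With 5 to 10 children symptomatic beforehand, Pearson gives 0.057 to 0.064 and Fisher 0.11 to 0.12, so the decision changes in both like-for-like pairs. With 0 to 4 beforehand, Pearson gives 0.008, 0.018, 0.030, 0.040 and 0.0495, all significant and in agreement with McNemar.

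**Example 2: four new symptoms, none beforehand.** Pearson 0.035 against asymptotic McNemar 0.046; Fisher 0.107 against exact McNemar 0.125. No decision changes.

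**Cross-tabulated layout, only if it was used.** At 30% prevalence with no change, it rejects in 17% of trials at ρ = 0.2 and 65% at ρ = 0.5. In the other direction, 10 new, 0 resolved, 1 both and 10 neither gives p = 0.33, against exact McNemar 0.002.

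**The case against.** The strongest reply is that no error is proven. The misapplied-test reading needs three things that the document leaves open: that the same children answered twice, that the wording excludes McNemar (whose statistic is itself referred to a chi-square distribution), and that answers were analysed as present/absent. The section is a short past-tense summary, and such summaries often omit the test variant. This stands as a limit on certainty. It does not remove the point, because the test as worded is not a test of within-child change, and even the benign reading leaves the safety test unnamed.

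The second reply is that the lost-sensitivity argument depends on the comparator. This also stands in part. Against exact McNemar, stacked Pearson has the higher power in every scenario tabulated above, and mid-p is below Pearson throughout the 5% to 30% scenario. The advantage of pairing is not confined to the asymptotic version, however: for a rise from 20% to 50% at ρ = 0.5, power is 56% for stacked Pearson, 64% for exact McNemar and 91% for asymptotic McNemar.

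Third, the changed decision in Example 1 needs a suitable number of children symptomatic beforehand; with 0 to 4 it does not occur. Fourth, the cross-tabulated figures have no support in the text and should carry no weight in judging severity. Both are accepted. Finally, the objectives sentence in the protocol names only pain, mobility and quality of life; safety enters under Outcomes. No efficacy result or sample size turns on this point.

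**Conclusion.** The point holds, with medium confidence. As written, the plan tests before/after change with a test for independent observations, and nothing in the document names a paired alternative. If McNemar was used, what remains is a naming fault. If an unpaired test was used on stacked answers, it is mainly conservative. On the assumptions stated, its false-positive rate falls below 1% at a correlation of 0.5. From a correlation of about 0.2 upward it has less power than the paired test of the same asymptotic kind, by 11.1 points (77.7 − 66.6) and 13.7 points (76.5 − 62.8) in the two scenarios at 0.3. With no symptoms beforehand, or correlation near 0, pairing changes little or slightly lowers power. Prevalence, correlation, scoring and layout are all undocumented, so the effect on the trial's reported safety result is unknown. It should be corrected because this is the only inferential safety analysis named.

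**What to change.** In the VR children, replace the chi-square test with McNemar's test if symptoms were scored present/absent, or with the Wilcoxon signed-rank test if questionnaire scores were analysed.

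State the McNemar version, since each has a price at n = 21. The asymptotic version is the like-for-like replacement: it gave at most 4.9% false positives for prevalence 5–50% and correlation 0–0.7, but can reach 7.8% if every child changes. Mid-p never exceeds 5.0% and exact never exceeds 3.2%, at a cost in power. That cost can put them below the chi-square when baseline symptoms are rare or correlation is low; the asymptotic version is also slightly less powerful at correlation 0.

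Report the counts of new and resolved symptoms with exact 95% intervals, whatever the p-value; for example, 6 new of 21 is 29%, interval 11% to 52%. State who completed the questionnaire, at which session or sessions, and how it was scored. If a between-group comparison of new symptoms was intended, say so.

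Cost: one line if McNemar was used. If an unpaired test was run on paired answers, re-analyse the existing data and correct the p-values. No new data are needed; McNemar uses only the two discordant counts.

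### The only safety analysis described, a pre/post significance test in 21 VR-exposed children, cannot bound the risk: up to 3 to 5 new cases could be non-significant, depending on the Chi-square version

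*Combined protocol and SAP*

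**What the plan says.** The last item under Outcomes makes safety an aim: "To evaluate the safety and satisfaction of fully immersive VR therapy in children with SCD". The Statistics section then gives one sentence on how it is analysed: SSQ outcomes were "analyzed using the Chi-square test to detect any significant changes in symptoms pre- and post-intervention". The 0.05 significance level "was used for all inferential statistical tests".

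On exposure, Methods says of the 42 children: "They were divided into an intervention group (group I, n=21) and a control group (group II, n=21". Group I had one 15-minute VR session in hospital. After discharge, "Group I participants received fully immersive VR for 40 minutes twice /week over three weeks (six sessions". For the control arm the text says only: "Yet, Group II received the prescribed drugs". So 21 children, with up to seven sessions each (1 + 6), carry all the information on VR-related sickness.

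Descriptive summaries are specified for demographic and baseline characteristics and for satisfaction, but not for safety. The plan gives no incidence of new symptoms, confidence interval, tolerable rate or rule for reading a non-significant result. It does not state which version of the Chi-square test was used, how symptoms were categorised, or which session or sessions the pre/post comparison covers.

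**The concern.** A safety aim asks how often the intervention makes a child feel worse, and how high that rate could plausibly be. A significance test of change answers neither question. It can flag a change, but a non-significant result in 21 children does not limit the risk.

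A pre/post test of this kind also responds to net change. A child whose symptom clears offsets a child whose symptom begins, although only the second has been harmed. Offsetting is plausible here because the first VR session takes place during hospitalization, when some children may already have symptoms. A correctly paired test does not remove the problem, so this point is separate from whether the Chi-square test respects the pairing.

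At stake is the safety statement the trial will make. If the p-value is all that is reported, a reader cannot tell evidence of a low sickness rate from a sample too small to show a moderate one.

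**Working it through.** **Plan's own figure.** There is none to reproduce: the document gives no safety threshold, power or expected rate.

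**Inputs from the document.** n = 21 exposed (Methods); level 0.05 and a Chi-square test (Statistics).

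**Assumptions.** Two-sided test; one symptom per child, scored present or absent; no missing data. For the base case, no child has the symptom before VR and none resolves. Let b be the number of children with a new symptom and c the number whose symptom resolves.

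**Step 1: largest b that stays non-significant.** The 5% critical value of chi-square on 1 df is 3.84. With 0/21 before and b/21 after:

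- Pearson, uncorrected: X² = 42b/(42 − b). b = 3 gives 126/39 = 3.23; b = 4 gives 168/38 = 4.42.
- Yates: X² = 42(b − 1)²/[b(42 − b)]. b = 5 gives 672/185 = 3.63; b = 6 gives 1050/216 = 4.86.
- McNemar, uncorrected: X² = (b − c)²/(b + c), which equals b when c = 0.
- McNemar, continuity-corrected: X² = (|b − c| − 1)²/(b + c). b = 5 gives 16/5 = 3.20; b = 6 gives 25/6 = 4.17.
- Exact McNemar with c = 0: p = 2 × 0.5^b.
- Fisher: p = 2 × C(21,b)/C(42,b).

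| Version | Largest non-significant b | p at that b | p at b + 1 |
|---|---|---|---|
| Pearson, uncorrected | 3 | 0.072 | 0.036 |
| McNemar, uncorrected | 3 | 0.083 | 0.046 |
| Fisher | 4 | 0.107 | 0.048 |
| Yates | 5 | 0.057 | 0.028 |
| McNemar, corrected | 5 | 0.074 | 0.041 |
| Exact McNemar | 5 | 0.0625 | 0.031 |

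**Step 2: what those counts leave open.** Clopper-Pearson 95% limits for x of n are the 2.5% quantile of Beta(x, n − x + 1) and the 97.5% quantile of Beta(x + 1, n − x).

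| New cases | Rate | Exact 95% CI |
|---|---|---|
| 0/21 | 0% | 0 to 16.1% |
| 3/21 | 14.3% | 3.0 to 36.3% |
| 4/21 | 19.0% | 5.4 to 41.9% |
| 5/21 | 23.8% | 8.2 to 47.2% |

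For 0/21 the upper limit is 1 − 0.025^(1/21) = 16.1%.

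**Step 3: symptoms at baseline, or symptoms that resolve.** For the unpaired tests the limit can rise with baseline symptoms. Under uncorrected Pearson with none resolving it is 4 new cases with 1 child symptomatic before VR, 5 with 2 to 4, and 6 with 5 to 10. For example, from 4/21 before, 9/21 after gives X² = 2.79 and 10/21 after gives X² = 3.86 (p = 0.0495).

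For the exact paired test, baseline symptoms that persist do not matter, but resolution does. Seven new and 1 resolved gives p = 2(1 + 8)/2⁸ = 0.070. Nine new and 2 resolved gives p = 2(1 + 11 + 55)/2¹¹ = 0.065. Six new and 2 resolved gives 0.29, and six new and 6 resolved gives 1.0.

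**Step 4: chance of significance in the base case.** With X ~ Binomial(21, π):

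| True onset rate π | P(X ≥ 4) | P(X ≥ 6) |
|---|---|---|
| 20% | 63% | 23% |
| 30% | 91% | 64% |

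The 4-case threshold belongs to the uncorrected tests; the 6-case threshold belongs to exact McNemar, corrected McNemar and Yates.

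**The case against.** The strongest reply is that the plan sets no decision rule. It uses the test to look for changes, and looking for changes is not a mistake. A reader might infer that the trial will call VR safe whenever p is at least 0.05; the document never says so, and that reading should not be attributed to it. What stands is the omission: no other analysis is described from which a safety conclusion could be drawn.

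A second reply is that the figure depends on the test. A reader might infer that 5 of 21 would always go unflagged. Under an uncorrected Pearson test with no baseline symptoms, arguably the plainest reading of the named method, 5/21 against 0/21 gives p = 0.017 and the limit is 3. This stands, so the size has to be given as a range with its test and assumptions named.

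Third, it would be too strong to say that an important sickness rate will usually be missed. The document defines no important rate, and at a true 20% onset rate the chance of significance is 63% or 23% according to the threshold.

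Fourth, the figures assume one dichotomised symptom per child, while the plan does not explain how symptoms were categorised or which of the seven sessions count. This too stands, and it binds the remedy as much as the criticism. Finally, safety is not among the aims in the objectives paragraph, which names pain, mobility and quality of life. That lowers the priority of the point without removing it, since Outcomes lists safety explicitly.

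**Conclusion.** The concern holds as a weakness in how the safety aim is analysed, not as a claim that the plan equates non-significance with safety. The one analysis described cannot bound the risk and offsets improvement against harm. Even at the lowest limit in the base case, 3 of 21, the result would be non-significant while compatible with a true rate of up to 36%; at the highest, 5 of 21, with up to 47%. These limits rest on the assumptions listed in the check and can be higher when children have symptoms beforehand or when symptoms resolve.

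The analysis should be changed, because a better one is available from the same data. The point does not affect the pain, mobility or quality-of-life comparisons.

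**What to change.** Base the safety conclusion on estimation:

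- For each SSQ symptom, and for any symptom, report the number and percentage of VR-exposed children whose symptom was new or worse after VR than before, with an exact (Clopper-Pearson) 95% confidence interval.
- Define the event per child: count a child once if it occurs at any session with SSQ data. State which of the seven sessions have such data and how many children contribute.
- Report improvements in a separate column and do not net them off.
- State the conclusion through the upper confidence limit, for instance that 0 of 21 remains compatible with a rate of about 16%. Do not infer safety from p ≥ 0.05.
- If a test is kept as a secondary analysis, make it paired (exact McNemar) and name it.

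The cost is revised wording in the Statistics section and one small table from SSQ data that the plan already describes; no further children or visits are needed. The drawback is a more cautious safety claim, because intervals from 21 children are wide.
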